5.5.1.1. Sensitivity Analyses of Primary Estimand

A sensitivity analysis will utilize multiple imputation (MI) under missing at random (MAR) assumption which uses all participants with available primary endpoint data through Day 29. The imputation model (using PROC MI) will be informed by the observed outcomes for participants through Day 29 including treatment and the prognostic factors listed above. Participants with missing information on the primary endpoint will be imputed using monotone logistic regression. Further variables will be considered for inclusion in the MI model on the basis they may inform missingness or be correlated with the endpoint. Missing outcomes will be imputed multiple=100 times. The seed for reproducibility will be set to 2020. The final analysis model applied to the complete data set will be the same as that for the primary analysis. Treatment

effect estimates from the individual completed data sets will be combined using Rubin's rules via PROC MIANALYZE.

A sensitivity analysis using control-based imputation will also be conducted. Missing primary endpoint status through Day 29 will be imputed using monotone logistic regression as stated above but informed only by the placebo group. This will be implemented by the MNAR statement with the option MODELOBS =(TRT=0), where TRT=0 indicates the placebo group.

Additional sensitivity analyses include:

- Repeat the primary efficacy analysis in the PPS analysis set.
- Repeat the primary efficacy analysis with baseline overall serostatus (categorical as positive; negative) as covariate instead of baseline qualitative serostatus. Any missing baseline overall serostatus will be imputed as positive.

5.5.2. Supplemental Estimand Analyses

[Appendix I](#) provides an overview of the main estimation and sensitivity analyses for the supplementary estimand (Estimand 1b). Estimand 1b utilizes a hypothetical strategy for the intercurrent event of receipt of prohibited treatments (refer to ADG20-TRMT-001 Designated Background Standard of Care document) for COVID-19 (IcEV3).

For participants with IcEv3, if the participant has not had a COVID-19-related hospitalization or death prior to the intercurrent event, the primary endpoint will be set to missing. Missing data for the supplementary analysis will be carried out using an MI based strategy that includes the following three steps:

- Step 1. Missing outcomes will be imputed multiple times ($M=100$) based on the intercurrent event handling strategy
- Step 2. The logistic regression analysis model presented above will be applied to each completed data set with terms including the prognostic factors and treatment variable and estimates of the treatment effect and associated standard error will be computed.
- Step 3. The individual completed sets will be combined using Rubin's rules to produce a single inferential statement (treatment effect, standard error, and p-value) via PROC MIANALYZE.

The imputation model will be informed by the observed outcomes from participants who either did not experience the intercurrent event or met the primary endpoint prior to receiving prohibited medication. The imputation model will include the prognostic factors as listed in Section [5.5.1](#). Further variables will be considered for inclusion in the MI model on the basis they may inform missingness or be correlated with the endpoint.

The final analysis model applied to the complete data set will be the same as that for the primary analysis.

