Participant Population: Mild or moderate COVID-19 in adults and adolescents can typically be managed in the outpatient/ambulatory setting. Data from other SARS-CoV-2 mAb programs suggest that populations at high risk for progression of COVID-19 are likely to benefit from treatment with a mAb (see Section 1.4.1). In order to ensure similar risk of COVID-19 disease progression across the two treatment groups, enrollment will be stratified based on age. Data from several regions have consistently shown that age is the most critical factor for risk of severe COVID-19 including hospitalization, ICU stay, and death ([Docherty 2020](#); [Grasselli 2020](#); [Ko 2020](#); [Wu 2020](#); [Kim 2021](#)). Of the risk factors identified, age appears to have the most profound impact on outcomes, with significant increase in risk clearly evident around age 65 and a greater magnitude in risk than that associated with any individual co-morbidity ([Kim 2021](#)). In a cohort of more than 1.3 million patients diagnosed with COVID-19, of patients with no reported underlying health conditions, 9.6%, 15.5%, and 27.9% of patients 50-59, 60-69, and 70-79 years of age required hospitalization, respectively ([Stokes 2020](#)).

Symptom Onset Within 5 Days: Symptoms of COVID-19 generally appear from 2 to 14 days following exposure to SARS-CoV-2. A subset of individuals with initially mild or moderate symptoms may experience disease progression. For example, in a study of 138 hospitalized patients with COVID-19 pneumonia, dyspnea, and hospitalization developed after a median of 5 and 8 days, respectively, from symptom onset ([Wang 2020](#)). These data suggest a window for intervention of <7 days from onset of symptoms with a potently neutralizing antiviral mAb like ADG20 to prevent disease progression. Consistent with this hypothesis, experience with other highly potent mAbs (casirivimab/imdevimab, bamlanivimab/etesevimab, sotrovimab,

regdanvimab, and bebtelovimab) suggests that administration early in the course of infection (eg, within 5 to 7 days or less of onset of symptoms) is associated with faster resolution of symptoms and a reduction in the need for medically attended visits, including emergency room visits and hospitalizations ([Celltrion Healthcare Hungary 2021](#); [Eli Lilly and Company 2022a](#); [Eli Lilly and Company 2022b](#); [GlaxoSmithKline 2022](#); [Regeneron 2022](#)).

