APPENDIX I. OVERVIEW OF STATISTICAL METHODS: ESTIMATIONS OF ESTIMANDS AND SENSITIVITY ANALYSES

Estimand Label	Estimand Description	Main Estimation			Sensitivity Analysis
		Analysis Set	Imputation/Data Handling Rules	Analysis Model/Method	
Estimand 1a	Treatment difference (ADG20 – Placebo) in proportion of COVID-19-related hospitalization or all-cause death through Day 29 regardless of intake of prohibited treatments for COVID-19	FAS	The endpoint will incorporate all available information through Day 29. Where participants have missing primary endpoint through Day 29, the status will be imputed as not having COVID-19-related hospitalization or all-cause death (ie, responder)	The endpoint will be analyzed using the methodology for determining a standardized estimator for a binary outcome, with adjustment for prognostic factors. The standard error of the standardized estimator will be estimated using the delta method (refer to Appendix K)	Multiple imputation under MAR assumption followed by calculation of standardized risk difference and 95% CI using Rubin's method. Control based imputation Per-protocol Set analysis
Estimand 1b	Treatment difference (ADG20 – Placebo) in proportion of COVID-19-related hospitalization or all-cause death through Day 29 assuming no intake of prohibited treatments for COVID-19	FAS	In case of prohibited treatments for COVID-19, the primary endpoint will utilize multiple imputation under MAR assumption. The imputation model will be informed by the observed outcomes from participants who did not receive such medication (or received it after meeting the primary endpoint). The logistic model will include the prognostic factors.	Same as Estimand 1a	Hypothetical strategy of handling the ICEs.
Estimand 2	Treatment difference (ADG20 – Placebo) in proportion of participants experiencing severe/critical COVID-19 or all-cause death through Day 29 in the target population	FAS	Same as Estimand 1a	Treatment difference in the proportion of participants with severe/critical COVID-19 or all-cause death through Day 29 will be presented and tested using the main analysis method outlined for Estimand 1a	

Estimand Label	Estimand Description	Main Estimation			Sensitivity Analysis
		Analysis Set	Imputation/Data Handling Rules	Analysis Model/Method	

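### The Estimand 1b imputation ignores event-free time observed before prohibited treatment, so the imputed event rates are biased; the effect on the treatment comparison can go either way

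*SAP*

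**What the plan says.** Estimand 1b supplements the primary estimand and asks what would have happened without prohibited COVID-19 treatment. SAP 5.5.2 handles that intercurrent event as follows: "if the participant has not had a COVID-19-related hospitalization or death prior to the intercurrent event, the primary endpoint will be set to missing". Appendix G lets the event start at any time from dosing through Day 29.

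The donors are specified: the model is "informed by the observed outcomes from participants who either did not experience the intercurrent event or met the primary endpoint" before the prohibited medication. So are the covariates: "The imputation model will include the prognostic factors as listed in Section" 5.5.1, that is, age, sex, serostatus, BMI and viral load. Treatment is not named here, although 5.5.1.1 names it for the primary estimand. One clause is left open: "Further variables will be considered for inclusion in the MI model on the basis they may inform missingness or be correlated with the endpoint". Appendix I states the assumption: "the primary endpoint will utilize multiple imputation under MAR assumption".

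The sensitivity analysis in 5.5.2.1 uses the same single regression, informed by placebo only. For participants with missing status under the primary estimand, 5.5.1.1 says: "Participants with missing information on the primary endpoint will be imputed using monotone logistic regression".

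**The concern.** Suppose a participant starts prohibited treatment on Day 10 without an event. Days 1-10 are known to be event-free, yet the whole Day 1-29 status is erased and redrawn at the risk of donors who include people hospitalized in those days. Missing at random means conditioning on what was observed, and the event-free days were observed.

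The donor rule adds to this. Participants with the event before any prohibited treatment stay in, while those event-free when they start it are removed. The donor event rate therefore exceeds the arm's true rate.

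Timing makes it relevant. Protocol 1.3.2 cites a cohort in which "dyspnea, and hospitalization developed after a median of 5 and 8 days, respectively, from symptom onset" (Section 1.2 gives 7 days for admission), and entry is within 5 days of onset. Much of the risk may therefore fall soon after dosing. At stake is whether Estimand 1b estimates what it claims to.

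**Working it through.** **Inputs.** From SAP 4.2: placebo rate 12%, relative risk reduction (RRR) 70%, so ADG20 0.30 × 12% = 3.6%; about 320 participants, taken as 160 per arm. Not in the documents, hence assumed: *f*, the share who start prohibited treatment in the window unless an event comes first; *s*, the share of 29-day risk elapsed by then; *h*, a multiplier on the remaining risk of those treated.

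**Anchor.** The SAP states about 80% power. The null SE is √(2 × 0.078 × 0.922/160) = 0.0300 and the alternative SE is √(0.12 × 0.88/160 + 0.036 × 0.964/160) = 0.0296. Power = Φ[(0.084 − 1.96 × 0.0300)/0.0296] = 80%. The rates reproduce the SAP's figure. No figure is given for Estimand 1b.

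**Formulas, per arm with 29-day risk *p*:**
- events observed: p[(1−f) + fs]
- share set to missing: f(1−ps)
- risk imputed as planned (donor risk): p[(1−f) + fs] / [(1−f) + fps]
- residual risk given event-free to that day: p(1−s)/(1−ps)

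Filling the missing share at donor risk makes the arm estimate equal the donor risk.

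**Placebo, f = 10%, s = 50%.** Observed 0.12 × 0.95 = 11.40%. Missing 0.10 × 0.94 = 9.40%. Imputed risk 0.1140/0.9060 = 12.58%. Residual risk 0.06/0.94 = 6.38%. About 160 × 0.094 = 15 participants are imputed, giving 15 × (0.1258 − 0.0638) ≈ 0.9 excess events. Using the residual risk returns 11.40 + 9.40 × 0.0638 = 12.0%.

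**Use 10% placebo / 4% ADG20, treatment in the model, true risk difference (RD) 8.40 points:**

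| s | Placebo residual risk | Placebo as imputed | ADG20 as imputed | RD | Overstatement |
|---|---|---|---|---|---|
| 10% | 10.93% | 12.12% | 3.61% | 8.50 | 1.2% |
| 25% | 9.28% | 12.29% | 3.64% | 8.66 | 3.1% |
| 50% | 6.38% | 12.58% | 3.67% | 8.91 | 6.1% |
| 80% | 2.65% | 12.93% | 3.72% | 9.21 | 9.7% |

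**Direction, all at s = 50%:**
- Equal use, 10% each: RD 8.79, RRR 69.9%. Use 20%/10% (placebo/ADG20): RD 9.51, RRR 71.5%. Use 5%/10%: RD 8.48, RRR 69.1%.
- Treatment left out of the imputation model, 10% each: pooled donor risk (11.40 + 3.42)/(90.60 + 90.18) = 8.20%. Placebo 12.17%, ADG20 4.23%, RD 7.95, RRR 65.3%.
- Prohibited treatment marks worsening, 10% each: the true RD is 8.82 at h = 2, 9.24 at h = 3 and 10.08 at h = 5. The planned method still gives 8.79. In placebo the two errors cancel at h of about 1.3, 2.0 and 3.9 for s = 25%, 50% and 75%.
- Control-based version, 10% each: ADG20 3.42 + 9.82 × 0.1258 = 4.66%, RD 7.93, RRR 63.0%.

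**The case against.** A reader might infer that the method inflates the effect in favour of ADG20. The documents do not support that. They give no rate of prohibited use by arm. With equal use RRR does not rise, and with treatment omitted, as 5.5.2 literally reads, the effect shrinks. Protocol 5.6.2.1 leaves rescue of non-hospitalized participants to the investigator's discretion, so it may track worsening. Full-window risk can then be too low rather than too high.

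That last point also bears on the remedy. Conditioning on event-free time with baseline factors alone returns 8.40 when the truth is 8.82 (h = 2) or 9.24 (h = 3), further off than the planned 8.79. This stands, and it is why the remedy must carry severity up to the intercurrent event. It does not rescue the plan, where one error would merely offset another by chance.

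The shift is also small: 0.39 points at 10% use in both arms and s = 50%, against a standard error near 3 points. Estimand 1b lies outside the testing hierarchy, and the control-based analysis pulls toward the null. All true, but that analysis also uses full-window risk and so does not test this assumption.

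The open clause on further variables could be read as permission to condition on time. It commits to nothing, and time to prohibited treatment is undefined for donors who never had it.

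For dropouts in 5.5.1.1 and 5.5.3.1 the case is weaker. Those are sensitivity analyses beside a main rule that counts missing status as no event.

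**Conclusion.** The defect is in the text: nothing in 5.5.2, 5.5.2.1 or Appendix I conditions on the event-free time already observed, and the donor pool is enriched for early events. If prohibited use is unrelated to remaining risk given treatment and baseline factors, and treatment is in the imputation model, event rates are overstated in both arms. The risk difference is then overstated by about 1-10% over the range of timing examined at 10%/4% use. Usage and timing are assumptions.

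The net direction for the treatment effect cannot be settled from the documents. It depends on the arm split, on whether prohibited treatment marks worsening, and on an imputation term that 5.5.2 leaves unnamed. The same paragraph, programmed two ways, gives an RD of 8.79 or 7.95 against a truth of 8.40 (10% use in both arms, s = 50%, h = 1). This is worth correcting before unblinding, at the weight of a supplementary analysis.

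**What to change.** In SAP 5.5.2 and 5.5.2.1:
- Impute only the period after the intercurrent event, conditional on being event-free to that day. Use either a discrete-time pooled logistic hazard or donors still event-free on that day.
- State that treatment is in the missing-at-random imputation model.
- Include COVID-19 severity recorded up to the intercurrent event alongside the baseline prognostic factors, in the imputation model only.
- For the control-based version, draw the later hazards from placebo.
- Align Appendix I. Extending the approach to dropouts in 5.5.1.1 and 5.5.3.1 is optional.

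No new data are needed. SAP 3.5.1 dates hospitalization by admission, Protocol 5.6.2 records medication dates, and Protocol 6.3.2.2 grades severity at each visit through Day 29. SAP 3.2 has the plan signed before unblinding. The cost is modest programming and a sparse hazard model: about 160 × 0.12 + 160 × 0.036 ≈ 25 events, so the intervals must be few. The primary test does not change.

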5.5. Efficacy Analyses

5.5.1. Primary Efficacy Analysis

The primary efficacy endpoint is the incidence of COVID-19-related hospitalization or all-cause death through Day 29 in the mFAS-non-Omicron analysis set. The null and alternative hypotheses are the following:

$$H_0: P_1 - P_0 = 0$$

$$H_1: P_1 - P_0 \neq 0$$

P_1 and P_0 are the proportion of participants with COVID-19-related hospitalization or all-cause death through Day 29 in the ADG20 and placebo groups respectively. Using the methodology as described below (with additional details in [Appendix J](#)), a standardized estimator for a binary outcome (standardized risk difference/standardized relative risk reduction) will be estimated with adjustment for the following prognostic factors: age (continuous), sex (categorical), baseline qualitative serostatus (categorical: positive, negative), BMI (continuous), and baseline viral load from NP sample (continuous as \log_{10} copies/mL). For all efficacy analysis models, missing baseline serostatus will be imputed as positive and missing baseline BMI and viral load will be imputed as the average of all participants with non-missing data at baseline. Age is a randomization stratification factor and, thus, cannot be missing.

[Appendix I](#) summarizes the main estimation and sensitivity analyses for the primary estimand (Estimand 1a). The main estimation for Estimand 1a will use available data for COVID-19 hospitalization or all-cause death through Day 29, implemented in the mFAS-non-Omicron analysis set. Missing status on COVID-19-related hospitalization or all-cause death will be imputed as not having a COVID-19 hospitalization or all-cause death. The number and percentages of participants who experience and do not experience a COVID-19-related hospitalization or all-cause death will be summarized by treatment group, including summaries of missing data, COVID-19-related hospitalizations, and all-cause death. The observed risk difference (placebo minus ADG20) with 95% CI (using the Miettinen-Nurminen method), observed relative risk reduction, standardized risk difference with 95% CI and associated p-values, and standardized relative risk reduction with 95% CI will be provided.

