The method described in [Ge et al. \(2011\)](#) computes a population-level estimate for the treatment difference (in terms of difference in proportion) and supports an adjustment for the pre-defined prognostic factors. The method relies on a logistic regression model that includes COVID-19-related hospitalization or all-cause death present or absent as the dependent variable and treatment and prognostic factors as independent variables. To define this model, consider the i th participant, $i = 1, \dots, n$, where n is the total number of participants, and let y_i denote the binary outcome for the primary endpoint (COVID-19-related hospitalization or all-cause death, present=1 or absent=0). The treatment indicator will be denoted by t_i , where $t_i = 0$ corresponds to the placebo arm and $t_i = 1$ corresponds to the treatment (ADG20) arm. The vector of prognostic factors for the i th participant will be denoted by \mathbf{x}_i . The model is given by:

$$\text{logit } p_i = \beta_0 + \beta_1 t_i + \boldsymbol{\beta}_2' \mathbf{x}_i,$$

where $p_i = P(y_i = 1)$, β_0 and β_1 are the intercept and slope, $\boldsymbol{\beta}_2$ is the vector of model parameters corresponding to the prognostic factors and the prime denotes transposition.

After the model has been fitted to the data, the model parameters will be estimated (the estimates will be denoted by $\hat{\beta}_0$, $\hat{\beta}_1$ and $\hat{\boldsymbol{\beta}}_2$, respectively). After that, two potential outcomes will be computed from the model for each participant. These outcomes represent the participant's outcomes if the participant has been assigned to the placebo and treatment arms:

$$p_{i0} = P(y_i = 1 | t_i = 0),$$

$$p_{i1} = P(y_i = 1 | t_i = 1).$$

The population-level estimates for the for the incidence rates will be defined as follows:

$$\hat{p}_0 = n^{-1} \sum_{i=1}^n p_{i0} \text{ and } \hat{p}_1 = n^{-1} \sum_{i=1}^n p_{i1}.$$

These estimates can be used to define an estimate for the treatment difference (difference in the incidence rates) or relative risk reduction in a straightforward manner, i.e.,

$$\hat{p}_1 - \hat{p}_0 \text{ and } 1 - \hat{p}_1/\hat{p}_0$$

The variance of the estimated treatment difference or relative risk reduction will be estimated using the delta method based on the algorithm presented in [Ge et al. 2011 \(Appendix J\)](#).

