5.5.2.1. Sensitivity Analyses of Supplemental Estimand

A sensitivity analysis using control-based imputation will be conducted. The analysis will impute the binary primary endpoint for participants who received prohibited medications to treat

COVID-19 using PROC MI. Missing primary endpoint status through Day 29 will be imputed using monotone logistic regression as stated in the sensitivity analyses for the primary analysis but informed only by the placebo group. This will be implemented by the MNAR statement with the option MODELOBS =(TRT=0), where TRT=0 indicates the placebo group.

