5.5.3.1. Sensitivity Analyses

For each of the two binary key secondary endpoints, sensitivity analyses will include MI under MAR, which uses all participants with available key secondary endpoint status through Day 29. The imputation model (using PROC MI) will be informed by the observed outcomes for participants through Day 29 including treatment and prognostic factors. Participants with missing information on each key secondary endpoint through Day 29 will be imputed using monotone logistic regression. Further variables will be considered for inclusion in the MI model on the basis that they may inform missingness or be correlated with the endpoint. The final analysis model applied to the complete data set will be the same as that for the primary analysis. Treatment effect estimates from the individual completed data sets will be combined using Rubin's rules via PROC MIANALYZE.

An additional sensitivity analysis will repeat the key secondary efficacy analyses in the PPS analysis set.

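### The Estimand 1b imputation model (SAP 5.5.2) does not name treatment; run as listed, it pulls the supplementary risk difference toward zero

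*SAP*

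**What the plan says.** Section 5.5.2 of the SAP estimates Estimand 1b under a hypothetical strategy for prohibited COVID-19 treatment. A participant who takes such treatment without an earlier COVID-19-related hospitalization or death has the endpoint set to missing. The imputation model is estimated from participants who did not take it, or who had their event first. No split by arm is stated. On the model's terms the text reads "The imputation model will include the prognostic factors as listed in Section" 5.5.1. That section lists age, sex, baseline qualitative serostatus, BMI and NP viral load.

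The SAP treats treatment as separate from that list:

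- Section 5.5.1 describes the analysis model as having "treatment and prognostic factors as independent variables".
- Step 2 of Section 5.5.2, the analysis applied after imputation, is specified "with terms including the prognostic factors and treatment variable".
- The MAR imputation model in Section 5.5.1.1 is "informed by the observed outcomes for participants through Day 29 including treatment and the prognostic factors listed above".
- The MAR imputation model in Section 5.5.3.1 is "informed by the observed outcomes for participants through Day 29 including treatment and prognostic factors".

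The Estimand 1b row of Appendix I also mentions only the prognostic factors. Section 5.5.2.1 adds a control-based sensitivity analysis, imputed by the same method "but informed only by the placebo group".

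**The concern.** Estimand 1b asks what the treatment effect would have been had nobody taken prohibited treatment. If the imputation model has no treatment term, two imputed participants with the same covariates receive the same event probability whichever arm they are in. That probability lies between the two arms' rates. Each arm is therefore pulled toward the other, and the analysis model, which does contain treatment, estimates a diluted effect.

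There is a second consequence. The placebo-only analysis is meant to show how the result moves under a more pessimistic assumption. If the main analysis already removes the treatment effect from imputed outcomes, the two can agree on the risk difference for a mechanical reason, and the agreement could be read as robustness.

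**Working it through.** **Inputs.** From SAP Section 4.2: placebo rate p0 = 0.12; relative risk reduction (RRR) 70%, so p1 = 0.3 × 0.12 = 0.036; about 320 participants, taken as 160 per arm under 1:1 randomization. The risk difference (RD, ADG20 minus placebo) is −8.4 points. The imputed shares, f0 on placebo and f1 on ADG20, are not in the documents and are assumed.

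**The plan's own figure.** For two proportions with a pooled null variance and pooled rate 0.078:

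[√160 × 0.084 − 1.96 × √(2 × 0.078 × 0.922)] / √(0.12 × 0.88 + 0.036 × 0.964) = (1.0625 − 0.7433) / 0.3746 = 0.852

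This gives power 80.3%, against the stated approximately 80%. The base case is sound.

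**Formulas, use unrelated to risk.**

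- Treatment in the model: imputed outcomes take their own arm's rate, so RD stays at −8.4 points and RRR at 70%.
- Treatment not in the model: imputed outcomes take the pooled donor rate, pool = [(1−f0)p0 + (1−f1)p1] / [(1−f0) + (1−f1)]. The arm rates become (1−f0)p0 + f0·pool and (1−f1)p1 + f1·pool. With f0 = f1 = f, pool = 0.078 and RD = (1−f)(p1−p0).
- Placebo-only (Section 5.5.2.1): the arm rates are p0 and (1−f1)p1 + f1·p0, so RD = (1−f1)(p1−p0).

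**Equal shares.** Arm rates are placebo / ADG20, in percent.

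| Imputed | No treatment term | RD, points | RRR | Placebo-only | RD, points | RRR |
|---|---|---|---|---|---|---|
| 5% | 11.79 / 3.81 | −7.98 | 67.7% | 12.00 / 4.02 | −7.98 | 66.5% |
| 10% | 11.58 / 4.02 | −7.56 | 65.3% | 12.00 / 4.44 | −7.56 | 63.0% |
| 20% | 11.16 / 4.44 | −6.72 | 60.2% | 12.00 / 5.28 | −6.72 | 56.0% |

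The two methods share the same expected RD but not the same RRR. The SAP also reports the latter: "standardized relative risk reduction with 95% CI will be provided".

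**Unequal shares.** With f0 = 15% and f1 = 5%: pool = (0.85 × 0.12 + 0.95 × 0.036) / 1.80 = 0.0757. RD without treatment = 0.0380 − 0.1134 = −7.5 points; placebo-only gives 0.95 × (−8.4) = −8.0 points. The analyses then differ, but both are nearer zero than −8.4.

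**Use rising with baseline risk.** This case was computed on expected outcomes for 200,000 records with five covariates, logistic imputation and the Appendix J standardization, with an assumed log-odds of use of 0.6 per SD of risk. RD without treatment is −7.8, −7.3 and about −6.3 points at 5%, 10% and 20%, a shrinkage of about 7%, 13% and 26%. With treatment in the model RD stays at −8.4.

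**Finite-sample check.** About 300 simulated trials per setting (n = 320, two covariates, 20 imputations, Rubin's rules) gave these mean risk differences in absolute points, with versus without treatment:

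- 5% imputed: 8.42 versus 7.97
- 10% imputed: 8.56 versus 7.70
- 20% imputed: 8.43 versus 6.68

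At 20% the share of trials with nominal p < 0.05 fell from 75.3% to 59.5%; at 5% it fell from 82.2% to 78.9%.

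**Scale.** The unadjusted standard error at 160 per arm is √[(0.12 × 0.88 + 0.036 × 0.964) / 160] = 2.96 points. The shifts of 0.42, 0.84 and 1.68 points are 0.14, 0.28 and 0.57 of it. A 5% share is 8 participants per arm.

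**The case against.** The text never says that only the prognostic factors enter the model, and it continues: "Further variables will be considered for inclusion in the MI model on the basis they may inform missingness or be correlated with the endpoint". Treatment is correlated with the endpoint under the trial's own hypothesis. Appendix I labels the Estimand 1b imputation as MAR, and the MAR model specified for this endpoint in Section 5.5.1.1 does name treatment. Elsewhere the SAP lists terms without treatment where it must be present, as in the Cox model of Section 5.5.3 and the AUC ANCOVA in Table 4. It is true that treatment is not explicitly excluded, and the harm arises only if the model is run as listed. But the further-variables sentence commits to nothing, and it also appears in Sections 5.5.1.1 and 5.5.3.1 beside a treatment term already named. The Cox and ANCOVA lists belong to analysis models that exist to compare the arms, so treatment is implied there. In an imputation model it is not.

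A second argument is that leaving treatment out could be right. Protocol Section 5.6.2.1 leaves rescue therapy outside hospital to the investigator's discretion, so users may be participants who are worsening. Suppose 10% of each arm are users with an untreated risk of 12% in both arms. The true difference is then 0.9 × (−8.4) = −7.56 points. The model without treatment returns that value, and the model with treatment returns −8.40. The arithmetic is correct, but the example needs users to differ from non-users beyond the model terms, which departs from the MAR assumption that Appendix I sets. The control-based analysis is the planned place to examine such departures.

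Third, the share may be small. Only use before an event counts, and the protocol describes alternative treatments as limited in availability. At 2%, about 3 participants per arm, the shift is 0.02 × 8.4 = 0.17 point, or 0.06 of a standard error. That stands, as does the point that the two expected risk differences coincide only with equal shares.

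**Conclusion.** The concern holds. Section 5.5.2 commits the Estimand 1b imputation model to a list without treatment, while the SAP's two other MAR imputation models name it. Run as listed, the model moves the risk difference toward zero whenever the arms differ. With equal shares and use unrelated to risk, the proportional loss equals the share imputed; it is larger if higher-risk participants use prohibited treatment more. With equal shares the placebo-only analysis then adds nothing on the expected risk difference, though the relative risk reductions still differ.

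The sizes rest on the SAP's 12% and 70% planning values and on assumed shares. The importance is moderate. Estimand 1b is supplementary and outside the testing hierarchy, the error is toward no difference, the primary result is unaffected, and Section 5.4.1 tabulates prohibited-medication use by arm. Because Section 3.2 requires the SAP to be signed before unblinding, the term should be settled in writing rather than left to programming.

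**What to change.** In Section 5.5.2, state that the imputation model includes treatment group together with the Section 5.5.1 prognostic factors, in line with Section 5.5.1.1. Say the same in the Estimand 1b row of Appendix I. Leave the placebo-only model in Section 5.5.2.1 as it is, so that it remains a distinct check. The cost is one phrase in two places and one additional variable in PROC MI; no new data are needed.
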